7.1.11 Assessment timelines

2, 2.5 hour assessments should be performed +/-15mins of the timepoint. PP100-01 treatment should be +/- 10mins of timepoint. 10, 20 hour assessments should be performed +/-30minutes of the timepoint.

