- 1. Start "loading" dose: 100 mg/kg NAC diluted in 200 ml diluent* i.v. over 2 hours
- 2. PP100-01 bolus infusion over 5 minutes
- 3. Second dose: 200 mg/kg NAC diluted in 1000 ml diluent* i.v. over 10 hours

* diluent is 5% Dextrose or 0.9% Sodium Chloride.

Investigational Medicinal Product: PP100-01 given as one dose after the initial "loading" dose with NAC.

- Group A: PP100-01 (2 µmol/kg calmangafodipir) after the "loading" dose of NAC
- Group B: PP100-01 (5 µmol/kg calmangafodipir) after the "loading" dose of NAC
- Group C: PP100-01 (10 μmol/kg calmangafodipir) after the "loading" dose of NAC

In each dosing cohort there will be 8 patients randomly allocated to PP100-01 and NAC (N=6) or NAC alone (N=2).

Patient population:

Any patient requiring treatment with NAC (confirmed by blood tests) for acute paracetamol/ acetaminophen overdose arriving to the hospital < 24hr after paracetamol/acetaminophen overdose (POD).

Study Purpose:

The study with PP100-01 in combination with NAC is designed to determine safety and tolerability of PP100-01 when co-administered with NAC as compared to the 12-hr NAC treatment regime for patients that come to the hospital after an overdose of paracetamol/acetaminophen.

As a secondary objective possible efficacy will be explored by using experimental biomarkers in serum/plasma, such as CK18 and microRNA MiR122, GLDH, mitochondrial DNA and others that might give efficacy signals for PP100-01. The diagnosis of paracetamol/acetaminophen overdose will be made by ALT and paracetamol/acetaminophen measurements.

This study includes several comparisons;

- Safety and tolerability of PP100-01 + NAC vs NAC alone
- Assess hepatotoxicity in patients after POD as assessed using ALT, INR and experimental biomarkers of liver damage

Primary Objective:

Investigate the safety and tolerability of PP100-01 add-on treatment to the 12hr NAC treatment regime in patients treated for paracetamol/acetaminophen overdose (POD) when NAC treatment is initiated before 24hours post POD.

Secondary Objective:

Determine if there is evidence of PP100-01 having efficacy with regard to treatment of paracetamol-induced liver injury by measurement of conventional clinical biomarkers and novel experimental biomarkers.

Study Design:

The study will be an open label, randomised, exploratory, rising dose design, NAC controlled, phase 1 safety and tolerability study in patients treated with NAC for paracetamol/acetaminophen overdose.

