Entry into the study will depend on the patient's blood results confirming the need for NAC. A total of 24 patients will be assigned into one of 3 dosing cohorts of 8 patients (N=6 for PP100-01 and NAC; N=2 for NAC alone).

The study will primarily evaluate safety and tolerability for treatment with PP100-01 in combination with NAC as compared to NAC alone.

Baseline Assessments:

Blood tests, vital signs, physical examination and an ECG will be completed as part of the baseline assessments.

NAC will be given to all patients arriving to the hospital according to the standard guidelines when paracetamol/acetaminophen overdose is suspected. All patients that arrive to the hospital within 24 hr of POD and require NAC treatment will be asked if they will participate in the study once their blood results are available. The following investigations will be performed as part of clinical care on arrival to hospital or 4hrs after overdose (whichever is the longer time):

- Paracetamol level in serum/plasma
- Urea and electrolytes and creatinine
- Liver function tests (LFTs) ALT, Bilirubin and ALP
- Clotting screen: INR and Prothrombin time (PT)

Treatment Phase:

Patients that have signed the informed consent will be treated with NAC and randomised to NAC alone (N=2 per dosing cohort) or PP100-01 and NAC (N=6 per dosing cohort)

- Group A: PP100-01 (2 µmol/kg calmangafodipir) after the "loading" dose of NAC
- Group B: PP100-01 (5 µmol/kg calmangafodipir) after the "loading" dose of NAC
- Group C: PP100-01 (10 µmol/kg calmangafodipir) after the "loading" dose of NAC

PP100-01 treatment is administered intravenously over 5 minutes.

The NAC regime will be continued with the second dose: 200 mg/kg NAC in 1000 ml i.v. over 10hr.

The following procedures should be performed during the treatment phase:

- ALT bilirubin and alkaline phosphatase (ALP)
- Prothrombin time and INR
- Serum creatinine
- Biomarkers: CK18 and microRNA MiR122, GLDH, mitochondrial DNA and others

End of treatment:

At the end of the 12hr NAC regimen the decision to continue NAC is made by:

- the ALT has more than doubled since the admission measurement, OR
- the ALT is two times the upper limit of normal or more, OR
- the INR is greater than 1.3 (in the absence of another cause, e.g. warfarin)
- paracetamol/acetaminophen concentration greater than 20 mg/mL

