7.1.3 Vital signs

Vital signs will be assessed at baseline (between 1 and 2 hrs after starting NAC) and again at 2.5, 10 and 20hrs after starting NAC. This will be recorded in the Case Report Form (CRF). The following vital signs will be evaluated in a supine position after at least 5 minutes of rest: blood pressure- systolic and diastolic (mmHg), heart rate (BPM), respiration rate (/min), pulse oximetry, temperature (°C) and temperature route.

Height (estimated) and weight will be collected at baseline.

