9 DOSAGE AND ADMINISTRATION

9.1 Dosing Regime Acetylcysteine (NAC)

Standard NAC regimen:

300 mg/kg NAC IV (200 mg/mL) in 5% glucose (dextrose) or 0.9% Sodium chloride over 12hr: 100 mg/kg in 200 mL over 2 hr ("loading dose"), then 200 mg/kg in 1000 mL over 10hr. Note that for patients weighing more than 110 kg, the dose will be calculated using a 110 kg weight as per the TOXBASE guidance.

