9.3 Dose Changes

Dose changes will not be allowed unless patients develop anaphylactoid reactions. These will be managed conventionally with temporary discontinuation of the infusion, symptomatic treatment as required and restarting at a lower rate once the reaction has subsided.

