12.3 Estimation of Sample Size

With the clinical safety data that are available we do not expect any adverse events but we note that PP100-01 has not been administered in paracetamol overdose patients treated with NAC. We deem that 6 patients per group in this initial dose escalation study will allow initial exploration of effects on biomarkers and potential dose limiting toxicity.

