4.6 Safety Secondary Outcomes (Safety population)

Vital signs (systolic blood pressure, diastolic blood pressure, pulse, respiratory rate, temperature, oxygen saturation) and haematology and clinical biochemistry parameters (PT, alkaline phosphatase, bilirubin, creatinine, haemoglobin, urea, MCV, WBC, sodium, potassium) will be summarised and analysed at their measurement time points using methods corresponding to those described in Section 4.5.

The ECG result (Normal / Abnormal Not Clinically Significant / Abnormal Clinically Significant) will be summarised by treatment group and overall at 2.5, 10 and 20 hours. The ECG summary results at each of these time points will also be cross-tabulated against the baseline ECG result, by treatment group and overall.

The number and proportion of participants who have anaphylactoid reactions recorded will be summarised by treatment group and overall in the same manner as for the primary outcome analysis in Section 4.4.

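### If the NAC loading dose ends more than 10 minutes late, the two PP100-01 timing rules conflict; if the site waits for it, a delay over 30 minutes puts the nominal 2.5 h ECG and vital signs before the drug.

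*Protocol*

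**What the plan says.** **Sequence.** The protocol synopsis describes "PP100-01 given as one dose after the initial" loading dose of NAC. Sections 5, 6.6.1, 7.1.7 and 9.2 repeat that order. Section 9.1 sets the loading dose at "100 mg/kg in 200 mL over 2 hr".

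**Clock.** Section 7.1.7 starts the clock with the first NAC bag and puts the sample taken just before PP100-01 at 2 h. The table in 7.2 has PP100-01 in the 2-hour column. Section 7.1.11 adds "PP100-01 treatment should be +/- 10mins of timepoint" and allows 15 minutes either side for the 2 h and 2.5 h assessments.

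**Interruption.** Under section 9.3, anaphylactoid reactions are managed by "temporary discontinuation of the infusion, symptomatic treatment as required and restarting at a lower rate once the reaction has subsided". SAP 4.3 has an adherence category for a NAC course completed with stops and restarts.

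**Readings.** Section 7.1.3 takes vital signs at baseline and "again at 2.5, 10 and 20hrs after starting NAC". Section 7.1.6 uses the same hours for the ECG. In SAP 4.6 the ECG result "will be summarised by treatment group and overall at 2.5, 10 and 20 hours", and each of those hours is cross-tabulated against baseline. Vital signs are analysed at their measurement time points by the methods of SAP 4.5.

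**Not stated.** No section says which timing rule prevails when the loading dose ends late. None ties the 2.5 h readings to the actual PP100-01 time. The SAP reports time from ingestion to PP100-01, but not time from PP100-01 to each reading.

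**The concern.** The 2.5 h reading is the only scheduled early blood pressure and ECG after the bolus; the next is at 10 h. Safety is the primary objective, and protocol section 2.3 lists an immediate fall in blood pressure among the important potential risks to be watched closely.

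If the loading dose runs late and the site holds PP100-01 until it finishes, the 2.5 h slot can pass before the drug is given. The patient then has a second pre-dose reading and nothing else scheduled for several hours. Following the SAP, that reading is tabulated at 2.5 h under a PP100-01 dose, and the ECG cross-tabulation compares two pre-dose results. An acute effect in that patient would be missed in these summaries and diluted in the group figure. The affected patient would typically be one who had just reacted to NAC.

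**Working it through.** **Inputs, in minutes from NAC start**
- Loading dose, uninterrupted: 0 to 120 (9.1).
- PP100-01 window: 120 ± 10 = 110 to 130 (7.1.7, 7.1.11, 7.2). Bolus length: 5 (7.1.7).
- 2.5 h readings: nominal 150, window 150 ± 15 = 135 to 165 (7.1.11). Next readings: 600.
- Patients: "A total of 24 patients will be assigned into one of 3 dosing cohorts of 8 patients", with 6 per cohort on PP100-01, so 3 × 6 = 18.

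**The plan's own timing, no interruption.** 120 + 600 = 720 minutes, the stated 12 hours. With the bolus it is 725, inside the stated ±30 minutes. A bolus started by 130 ends by 135, when the 2.5 h window opens. With no delay the schedule works.

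**Loading dose ends d minutes late and the site waits.** PP100-01 starts no earlier than 120 + d and ends no earlier than 125 + d.
- Dosing window met: 120 + d ≤ 130, so d ≤ 10.
- Nominal 2.5 h reading after the bolus has ended: 125 + d ≤ 150, so d ≤ 25.
- Nominal reading before the bolus starts: 150 < 120 + d, so d > 30.
- Some part of the 2.5 h window after the bolus has ended: 125 + d ≤ 165, so d ≤ 40.
- Whole window before the bolus starts: 165 < 120 + d, so d > 45.

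| Delay d (min) | PP100-01 window | Reading at nominal 2.5 h |
|---|---|---|
| up to 10 | met | after the bolus |
| over 10 to 25 | missed | after the bolus |
| over 25 to 30 | missed | during the bolus |
| over 30 to 45 | missed | before the bolus |
| over 45 | missed | before the bolus, as is the whole window |

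**How large d might be.** The documents give neither pause length nor restart rate, so these are assumptions. With restart at a fraction r of the first rate, d = pause + remaining time × (1/r − 1).
- 10 min pause, r = 1: d = 10. Both rules met.
- 10 min pause, half infused (60 min left), r = 0.75: d = 10 + 20 = 30.
- 30 min pause, half infused, r = 0.75: d = 30 + 20 = 50. The bolus starts at 170 (2 h 50), after the window closes, and the next reading is 600 − 170 = 430 minutes later (7 h 10).
- 30 min pause, half infused, r = 0.5: d = 30 + 60 = 90.

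Across pauses of 10 to 60 minutes, r of 0.5 to 1 and 10% to 90% already infused, d runs from 10 to 168.

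**How often.** Protocol section 2.2.2 gives anaphylactoid rates of 14% to 18% on regimens with a 150 mg/kg loading dose. Section 3.2 says the 12-hour regimen reduced these, without a figure. For an assumed rate p, the chance of at least one reaction in 18 patients is 1 − (1 − p)^18.

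| Assumed p | Chance of at least one | Expected number (18p) |
|---|---|---|
| 2% | 0.305 | 0.36 |
| 5% | 0.603 | 0.9 |
| 10% | 0.850 | 1.8 |
| 15% | 0.946 | 2.7 |

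This counts all reactions. Those after the loading dose, and pauses that add little delay, do not cause the problem, so the figures are upper bounds. One affected patient is 1/6 = 17% of a dose group's 2.5 h data.

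**The case against.** The case against is fair on several points.

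- **Most of the time there is no conflict.** A reader might infer that any interruption breaks the plan. It does not: up to 10 minutes' delay satisfies both rules, and up to 25 minutes the nominal 2.5 h reading still follows the bolus.
- **The early edge of the window is not a contradiction.** A reader might note that the window opens at 1 h 50, before a 2-hour loading dose ends. Read together, the rules leave 2 h 00 to 2 h 10, and a site can obey both.
- **Acute safety is not left unobserved.** Adverse events, the primary outcome, are recorded from consent to discharge (10.3) and listed with start date and time (SAP 4.9). Section 7.1.7 asks for precautions and monitoring during administration, although its vital-sign reference leads back to 7.1.3 and so to the NAC clock.
- **The data allow tracing.** SAP 4.3 already needs the start times of NAC and PP100-01, and stops are tabulated and listed. In groups of six an affected patient can be found. PP100-01 might also not be given at all, which the SAP provides for.
- **The wording is 'should', and deviations are recorded.** That softens the rule but does not settle it. Section 16.2 requires prior agreement for deviations except for immediate hazard, which suits a foreseen event poorly. Listing a deviation also does not reclassify the reading.

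These points limit the reach of the concern. None supplies a governing rule or tells the analyst how to class a 2.5 h reading taken before the bolus.

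**Conclusion.** The point holds in conditional form. With a delay over 10 minutes the two timing rules cannot both be met, and the documents do not say which governs. If the site waits, the nominal 2.5 h ECG and vital signs precede PP100-01 beyond 30 minutes, and the whole window does beyond 45. The thresholds follow from the protocol's own times; the site waiting is an assumption. That such delays are plausible rests on assumed pauses and restart rates.

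The 30% to 95% range should not be read as the probability of a misclassified reading. It is the chance of at least one reaction of any timing, at assumed rates of 2% to 15%. The documents support no estimate for the 12-hour regimen. The consequence is confined to the scheduled ECG and vital-sign summaries and does not reach the adverse-event outcome. In those summaries one patient is a sixth of a dose group, so the gap should be closed.

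**What to change.** 1. **SAP 4.6.** Use the recorded PP100-01 start time to report the time from PP100-01 to each ECG and vital-sign reading. Class any reading taken before the bolus as pre-dose and not as a 2.5 h on-drug value. SAP 4.3 already needs the start times, so this costs about one sentence and a derived variable.
2. **Protocol.** Reconcile 7.1.3, 7.1.6, 7.1.7, 7.1.11, 7.2, 9.2 and 9.3 so that one timing rule applies when the loading dose is interrupted, and so that the assessment meant to follow PP100-01 is tied to its actual administration. The sponsor decides the rule and the interval. This needs amendment wording but adds no assessments.

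The downside is small: in the few affected patients the reading falls at a different nominal clock time from the rest of the group.

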7.2 Table of Assessments

Visit windows	Screen ing	0 (NAC treatment)	Baseline (Pre-PP100-01)	After 2 hrs	After 2.5 hrs	After 10 hrs	After 12 hrs	After 20 hrs	Discharge after 22 hrs	7 day follow up	30 day follow up	90 day follow up
Informed Consent	Х											
Eligibility Criteria	Х											
Enroled into trial	Х											
Treatment Allocation/randomisation	Х											
Bloods												
APAP conc level	Х					х		Х				
INR /Prothrombin	Х			Х		Х		Х				
ALT (IU/L)	Х			Х		х		Х				
ALP (IU/L)	Х			Х		Х		Х				
Bilirubin	Х			Х		Х		х				
Creatinine	Х			Х		Х		Х				
Hb	Х					Х		Х				
Urea	Х					х		Х				
Sodium	Х					х		Х				-
Potassium	Х					Х		Х				
MCV	Х					х		Х				
WBC	Х					Х		Х				
Inflammation Biomarkers				Х		Х		Х				
PP100-01 levels				Х		Х		Х				
Pregnancy test	Х											
Treatment												
NAC Treatment		Х			Х		(X)	(X)				
PP100-01 Treatment				Х					1		1	
Physical Examination			х	X*	X*	Х*		X*	1		1	
ECG			Х		Х	х		Х				
Vital signs (BP and P)			Х		Х	Х		х				
Adverse events			Х	Х	Х	х		Х	х	Х	Х	Х

*If AEs/SAEs identified that require a full physical exam to be completed (x) NAC continued as per TOXBASE (12hours +/-30mins). 2, 2.5 hour assessments should be performed +/-15mins of the timepoint. PP100-01 treatment should be +/- 10mins of timepoint. 10, 20 hour assessments should be performed +/-30minutes of the timepoint.

8 STUDY MEDICATION

8.1 Study Medication 1, PP100-01

PP100-01, calmangafodipir in concentration 50 mM (corresponding to 10 mM Mn II) is an aseptically prepared, sterile filtered product. PP100-01 is provided as a sterile, bright yellow clear solution in 20 ml single dose glass vials. The pH is adjusted between 7.4 and 7.6 with sodium hydroxide to protect against hydrolysis.

8.1.1 Receipt of PP100-01

The active ingredient, calmangafodipir, is manufactured at Albany Molecular, Research Inc. (AMRI), Albany NY, USA. The final IMP (PP100-01) will be manufactured, packed and labelled at Recipharm Pharmaceutical Development AB, Solna Sweden.

PP100-01 will be supplied to each site already packaged and labelled. IMP will be shipped to the local depot to be further sent to the hospital pharmacy or directly to the hospital pharmacy. All used and unused IMP must be kept at the site for accountability purposes.

8.1.2 Packaging and labelling of PP100-01

PP100-01 is packaged in kits each containing solution in 20 ml glass vials that are to be stored and transported frozen.

The glass vials will be labelled in English.

8.1.3 Storage and handling

PP100-01 should be stored in a safe place with limited access. PP100-01 is to be protected from light and stored at -15 to -25°C. Maintenance of a temperature log is mandatory. The log should be updated by delegated site personnel twice per week.

PP100-01 should be thawed by holding it in a hand for at least 5 minutes to defrost it. The thawed vial is stable when stored in refrigerator for up to 6 days prior to use. PP100-01 may be thawed and refrozen once, but this should be avoided. Temperature logs must be kept for the freezer and refrigerator where the PP100-01 is stored. The temperature should be noted twice weekly (unless automatic temperature readings are available).

8.1.4 PP100-01 accountability

It is the responsibility of the Investigator to establish a system for handling the PP100-01, to ensure that:

- Deliveries of such products are correctly received and recorded by a designated person
- PP100-01 is handled and stored safely and properly
- PP100-01 is given only to study patients in accordance with the CSP
- All unused PP100-01 and empty containers are stored until they have been checked by the monitor
- It is possible to reconcile records of all used and unused stocks as confirmed by Investigator's signature

The monitors should account for all PP100-01 at the study site. Used PP100-01 vials will be accounted and disposed at the sites. Unused PP100-01 vials should be kept and sent for destruction.

8.1.5 Assessment of PP100-01 compliance

Assessment of patient compliance is not applicable as the PP100-01 is administered at the clinic by a study nurse as an infusion. The investigator has the responsibility to document all PP100-01 dispensed in the accountability log and in the medical records.

8.1.6 **Procedure for preparation of patient dose:**

Doses of PP100-01 are based on the patient's weight and therefore infusions need to be prepared individually for each patient. At the study site, the PP100-01 should be prepared immediately before each patient administration according to procedure for preparation of the PP100-01.

Any unused Product should be destroyed according to local requirements and regulations. The PP100-01 will be supplied to the clinical study sites as a 50 mM calmangafodipir concentrate for solution for intravenous infusion.

The preparation process will be performed as described below and should be repeated before each administration:

- 1. Patient is weighed and the weight is documented in the patients CRF.
- 2. Based on the weight of the patient and the current applicable dose step, the dose is calculated:
 - 2 µmol/kg calmangafodipir dose will be 0.04 mL/kg
 - 5 µmol/kg calmangafodipir dose will be 0.10 mL/kg)
 - 10 µmol/kg calmangafodipir dose will be 0.20 mL/kg)
- 3. Dose will be documented in the patients CRF. The research staff will prepare PP100-01 solution with a dose as calculated in point 2 above, and record the volume. This solution is made up to a final volume of 20mL with normal saline. Volume over 20mL will not require the addition of normal saline. The solution is aspirated into a suitable syringe. The PP100-01 solution in the syringe is stable for 3 hours in ambient conditions and 6 hours when refrigerated.

8.1.7 Investigator's Brochure

The Investigator's Brochure is given in Appendix A.

8.2 Study Medication 2, N-acetylcysteine

8.2.1 Study Drug Identification

Acetylcysteine, trade name of Parvolex

8.2.2 Study Drug Manufacturer and Marketing Authorisation Holder

UCB Pharma Limited [name]

Marketing Authorisation: PL 00039/0410

8.2.3 Labelling and Packaging

Acetylcysteine for use in the study will be available as 10 mL ampoules containing 200 mg/mL acetylcysteine.

The acetylcysteine will be taken from existing hospital stock.

8.2.4 Storage

Acetylcysteine ampoules will be stored in a cupboard at the study site.

8.2.5 Summary of Product Characteristics

The Summary of Product Characteristics (SoPC) is given in Appendix B

9 DOSAGE AND ADMINISTRATION

9.1 Dosing Regime Acetylcysteine (NAC)

Standard NAC regimen:

300 mg/kg NAC IV (200 mg/mL) in 5% glucose (dextrose) or 0.9% Sodium chloride over 12hr: 100 mg/kg in 200 mL over 2 hr ("loading dose"), then 200 mg/kg in 1000 mL over 10hr. Note that for patients weighing more than 110 kg, the dose will be calculated using a 110 kg weight as per the TOXBASE guidance.

9.2 Dosing of PP100-01

- Group A: PP100-01 (2 μmol/kg calmangafodipir) after the "loading" dose of NAC
- Group B: PP100-01 (5 µmol/kg calmangafodipir) after the "loading" dose of NAC

Group C: PP100-01 (10 µmol/kg calmangafodipir) after the "loading" dose of NAC

9.3 Dose Changes

Dose changes will not be allowed unless patients develop anaphylactoid reactions. These will be managed conventionally with temporary discontinuation of the infusion, symptomatic treatment as required and restarting at a lower rate once the reaction has subsided.

9.4 Participant Compliance

The study drugs will be administered by nursing staff either as a single intravenous bolus or as an infusion. Treatment will be supervised in hospital by a clinician.

